### 6.11.2.6 Recurrence-free Survival (RFS) by Investigator

RFS by investigator is defined similar to the primary endpoint, but recurrence and new primary melanoma are decided by Investigator. It is defined as the time between the date of randomization and the date of first recurrence (local, regional, or distant metastasis by investigator), new primary melanoma (by investigator), or all-cause death, whichever occurs first. (Note: a patient who dies without reported recurrence will be considered to have recurred on the date of death.) For patients who remain alive and whose disease has not recurred, RFS will be censored on the date of last evaluable disease assessment. For those patients who remained alive and had no recorded post-randomization tumor assessment, RFS will be censored on the day of randomization. Censoring rules for the primary analysis of RFS are presented in [Table 5](#).

**Table 5 Censoring Scheme for RFS**

Situation	Date of Event or Censoring	Outcome
Recurrence (local, regional, distant, new primary melanoma)	Date of first recurrence	Event
Death without recurrence	Date of death	Event
No baseline disease assessment	Date of randomization	Censored
No on-study disease assessments and no death	Date of randomization	Censored
No recurrence and no death	Date of last evaluable disease assessment	Censored
New anticancer therapy (for melanoma or second non-melanoma primary cancer), including melanoma tumor-directed radiotherapy and melanoma tumor-directed surgery, received without recurrence reported prior to or on the same day of disease assessment	Date of last evaluable disease assessment prior to or on the same date of initiation of subsequent therapy	Censored

The RFS by investigator in the Safety population will be conducted by summarizing the number of events, and the descriptive statistics (median and its 95% CI, Q1, Q3, minimum, maximum) based on the Kaplan-Meier estimate will also be summarized by treatment arm. The RFS rates at 6 and 12 months will be presented by treatment arm.

## 7.0 SAFETY ANALYSIS

The safety data will include AEs and SAEs. Summaries will use Safety population and will be performed separately by treatment arm. All safety data will be presented in data listings.

### 7.1 Adverse Events

Adverse events will be coded by system organ class (SOC) and preferred term (PT) using MedDRA. Adverse event severity will be based on NCI CTCAE Grade (version 5.0).

All AEs will be coded by MedDRA version 21.1. The severity of AE will be determined based on the National Cancer Institute Common Terminology Criteria for Adverse Events (NCI CTCAE) Grade (version 5.0). An AE is considered as related to treatment if it is related to any study drug; an AE with a missing relationship will be counted as related to study drug. An AE is considered as leading to treatment discontinuation if it is leading to discontinuation of any study drug. An AE is considered as leading to treatment delay, reduction or interruption if reported as leading to the dose delay, reduction or interruption of any study drug. An AE is considered as leading to death if the severity grade is 5 or the outcome is fatal. A patient reporting the same AE multiple times will be counted only once within each SOC and PT under the highest severity and closest relationship.

The following adverse events summaries will be provided by treatment arm:

- Overall summary of TEAEs
- TEAEs presented by worst CTC grade (any grade, grade 3-4, grade 5) by SOC and PT
- Serious TEAEs presented by worst CTC grade (any grade, grade 3-4, grade 5) by SOC and PT
- Drug-related TEAEs presented by worst CTC grade (any grade, grade 3-4, grade 5) by SOC and PT
- TEAEs leading to any study drug discontinuation presented by worst CTC grade (any grade, grade 3-4, grade 5) by SOC and PT
- TEAEs leading to death presented by worst CTC grade (any grade, grade 3-4, grade 5) by SOC and PT
- Grade 3 or above TEAE by by SOC and PT

All AEs will be presented in listing as follows:

- All TEAEs
- SAEs
- Grade 3 or above TEAEs
- TEAE leading to any study drug discontinuation
- TEAEs leading to death

## 7.2 Immune Mediated Adverse Events (IMAEs)

Immune-mediated AEs (IMAE) are AEs consistent with an immune-mediated mechanism or immune-mediated component for which non-inflammatory etiologies (eg, infection or tumor progression) have been ruled out. IMAEs can include events with an alternate etiology which were exacerbated by the induction of autoimmunity. To be specific, IMAEs are events (or groups of PTs describing specific events) that include pneumonitis, diarrhea/colitis, hepatitis, nephritis/renal dysfunction, rash, endocrine (adrenal insufficiency, hypothyroidism/thyroiditis, hypothyroidism, thyroiditis, hyperthyroidism, diabetes mellitus and hypophysitis), and other specific events, considered as potential immune-mediated events by investigator that meet the definition summarized below:

- those occurring within extended treatment-emergent period,
- regardless of causality,
- treated with immune-modulating medication (of note, endocrine AEs such as adrenal insufficiency, hypothyroidism/thyroiditis, hypothyroidism, thyroiditis, hyperthyroidism, diabetes mellitus, and hypophysitis are considered IMAEs regardless of immune-modulating medication use, since endocrine drug reactions are often managed without immune-modulating medication),
- with no clear alternate etiology based on investigator assessment, or with an immune-mediated component

The list of MedDRA preferred terms used to identify IMAEs is revisited quarterly and updated accordingly. The preferred terms used for the selection at the time of the database lock by categories will be provided. IMAEs will be summarized using the extended treatment-emergent period by treatment arm for each immune-mediated category:

- Overall summary of non-endocrine IMAEs by worst CTC grade (any grade, grade 3-4, grade 5) where immune modulating medication was initiated presented by Category / PT.

- Overall summary of endocrine IMAEs by worst CTC grade (any grade, grade 3-4, grade 5) presented by Category / PT

A by-patient listing of IMAEs will be provided.

### **7.3 Other Immune-Related Adverse Events of Special Interest (OirAESIs) for Checkpoint Inhibitors**

Other immune-related events of special interest (OirAESIs) for checkpoint inhibitors consist of a list of preferred terms grouped by specific category (e.g., Myositis Event, Myocarditis Event, Demyelination Event, Guillain-Barre Syndrome, Pancreatitis Event, Uveitis Event, Encephalitis Event, Myasthenic Syndrome, Rhabdomyolysis Event, Graft Versus Host Disease).

The list of MedDRA preferred terms used to identify OirAESI is revisited quarterly and updated accordingly. The preferred terms used for the selection at the time of the database lock by categories will be provided.

OirAESIs will be summarized by treatment arm for each category. The following analyses will be conducted using the extended treatment-emergent period:

- Overall summary of OirAESIs by worst CTC grade (any grade, grade 3-4, grade 5) presented by Category / PT

A by-patient listing of OirAESIs will be provided.

### **7.4 Adverse Events of Special Interest for bempegaldesleukin (NKTR-214)**

Adverse events of special interest for bempegaldesleukin (NKTR-214) consists of ischemic cerebrovascular events (ICE). All analyses will be conducted in the Safety population by treatment arm using the treatment-emergent period. Search list used to identify ICE will be provided.

The following analyses will be conducted for ICE:

- Overall summary of ICE by worst CTC grade (any grade, grade 3-4, grade 5) presented by PT

A by-patient listing of ICE will be provided.

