## 6.6 Definitions

- **Baseline:** In general, baseline will be defined as the last assessment result on or before the randomization date (and time if available).

Pre-treatment AEs will be defined as AEs with an onset date prior to but not including the day of the first dose of study treatment.

- **Study Day:** There is no study day zero. In general, Study Day 1 is the date of randomization.
  - For post-randomization days, study day is calculated as: assessment date – randomization date + 1
  - For pre-randomization days, study day is calculated as: assessment date – randomization date

For safety analysis, study day is calculated and presented based on first dose date as defined below.

- **First Dose Date:** First dose date will be defined as the date of first dose, Cycle 1 Day 1 (C1D1). Note, per protocol, first dose date may be  $\leq 5$  days after the date of randomization. If randomization date and first dose date is not on the same day, then date of randomization will be different from C1D1. Safety data will be calculated and presented based on First Dose Date.
- **Treatment-emergent/Extended Treatment-emergent Period:**

For patients on treatment, both the treatment-emergent period and extended treatment-emergent period will be defined as the period of time on or after the day (and time, if collected and not missing) of the first dose of study treatment.

For patients off treatment, the treatment-emergent period is defined as the period of time on or after the day (and time, if collected and not missing) of the first dose of study treatment, until: earlier date of (initiation of new anticancer therapy – 1 day) and (30 days after the date of the last dose of any study treatment).

The extended treatment-emergent period will be defined as the period of time on or after the day (and time, if collected and not missing) of the first dose of study treatment, until earlier date of (initiation of new anticancer therapy – 1 day) and (100 days after the date of the last dose of any study treatment)

- **Treatment-Emergent Adverse Event (TEAE):**

TEAEs are AEs with onset date (and time, if collected and not missing) within the treatment-emergent period, or extended treatment-emergent period depending on the analysis

Incomplete start and end date for TEAEs will be imputed. Any AE will be considered as a TEAE if its status cannot be fully determined because of incomplete data.

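### SAP 7.4 summarises the bempegaldesleukin AESI only to 30 days after last dose, although events are collected to 100 days and SAP 7.2 and 7.3 use the 100-day period

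*SAP*

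**What the plan says.** SAP 7.4 takes ischemic cerebrovascular events (ICE) as the AESI for bempegaldesleukin and sets the window: "All analyses will be conducted in the Safety population by treatment arm using the treatment-emergent period". On how events are identified it says only: "Search list used to identify ICE will be provided".

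SAP 6.6 defines two periods. Both start at first dose. For a patient off treatment, both stop at the day before new anticancer therapy if that comes first. Otherwise the treatment-emergent period ends "30 days after the date of the last dose of any study treatment" and the extended period ends "100 days after the date of the last dose of any study treatment". A treatment-emergent AE may fall in the first period "or extended treatment-emergent period depending on the analysis".

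The two sections just before 7.4 choose the longer period. For immune-mediated AEs, SAP 7.2 states: "IMAEs will be summarized using the extended treatment-emergent period by treatment arm". For other immune-related events, SAP 7.3 states: "The following analyses will be conducted using the extended treatment-emergent period".

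In the protocol, Section 8.10 lists a single AESI, CVA events of any grade. Section 8.5 collects AEs to 100 (± 7) days after last dose. Section 8.7 collects SAEs over the same span whether or not other anticancer therapy has begun.

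**The concern.** CVA became an AESI because of events in this development program. Protocol 2.1.3.2.5.2 reports 26 of 1345 exposed patients, 13 with Grade 3 or 4 events and 4 with a fatal outcome. First events occurred between day 4 and day 727. It is then odd that the one AESI named in the protocol gets the shorter window while the immune-related categories get the longer one.

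Early termination does not explain the choice. SAP 3.0 and 4.0 list the analyses dropped for that reason. The AESI summary is not among them, and a shortened window is not mentioned.

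What is at stake is the completeness of one descriptive safety table. An event that starts on days 31 to 100 after last dose, with no new anticancer therapy, is collected but left out of the by-arm AESI summary. No other planned table is stated to give a by-arm AESI total over 100 days.

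**Working it through.** The plan gives no figure to reproduce. The check covers the direction, the length of time left out, and an illustrative size.

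**Direction.** Let L be the day of last dose and N the day new anticancer therapy starts. The 7.4 window closes at min(N − 1, L + 30) and the extended window at min(N − 1, L + 100). The first is never later than the second, so every event counted under 7.4 is also counted in the extended period. The 7.4 count is lower or equal. For patients still on treatment the two periods coincide.

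**Time left out, no new therapy.**
- Completer on schedule: last dose on day 1 + 16 × 21 = 337 in Arm A (17 cycles) and 1 + 12 × 28 = 337 in Arm B (13 cycles). The windows close on day 367 and day 437. The 70 days left out are 70/437 = 16% of the extended window.
- One dose only: the windows close on day 31 and day 101, and 70/101 = 69% is left out.

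**Illustrative number of Arm A events left out.** Inputs:
- about 774 patients enrolled (SAP 5.1), assumed all randomized 1:1 and treated, so 774/2 = 387 in Arm A;
- CVA rate with bempegaldesleukin plus nivolumab, 19/1116 = 1.7% (protocol 2.1.3.2.5.2), taken as the full Arm A risk;
- time to first CVA, mean 218.7 and median 158 days (same section), assumed to run from first dose and to keep its pattern after dosing stops;
- early-stopping values of L: median exposure of 106 days (all regimens) and 101 days (doublet) in PIVOT-02 (protocol 2.1.3.2.2).

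Expected Arm A CVAs: 0.01703 × 387 = 6.59.

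Events left out = 6.59 × [F(L + 100) − F(L + 30)]. F is either exponential with mean 218.7, or lognormal with median 158 and σ = √(2 ln(218.7/158)) = 0.806.

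- L = 337, exponential: 0.8644 − 0.8133 = 0.0511, or 0.34 events. Lognormal: 0.8965 − 0.8520 = 0.0444 (from unrounded values), or 0.29 events.
- L = 106, exponential: 0.6101 − 0.4631 = 0.1471 (unrounded), or 0.97 events. Lognormal: 0.6289 − 0.4262 = 0.2027, or 1.34 events.
- L = 101, exponential: 0.6011 − 0.4506 = 0.1505, or 0.99 events. Lognormal: 0.6173 − 0.4081 = 0.2092, or 1.38 events.

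With 300 treated Arm A patients, expected CVAs are 0.01703 × 300 = 5.11. The range is then 5.11 × 0.0444 = 0.23 to 5.11 × 0.2092 = 1.07.

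**The case against.** The strongest reply is that no analysis rule is broken. Protocol 8.10 is a 24-hour reporting rule, 8.5 and 8.7 set collection periods, and 9.7 prescribes neither an AESI analysis nor a 100-day summary. An analysis window may be shorter than a collection window, and SAP 6.6 leaves the choice to each analysis. This stands: the point is an unexplained difference inside the SAP, not a contradiction of the protocol. It does not supply a reason for the shorter window.

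Second, that a shorter nested window cannot raise a count is true by construction, and the counts may be equal. The 30 days also run from the last dose of any study treatment. An Arm A patient who stops bempegaldesleukin but continues nivolumab therefore stays in the window. Both points stand and limit the size.

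Third, there is other cover. SAP 7.1 tabulates events by arm and preferred term without naming the window, its SAE listing is not labelled treatment-emergent, and SAP 7.0 promises that all safety data will be listed. Single late events may be visible there. What is still missing is a by-arm AESI total over 100 days.

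Fourth, the upper illustration borrows exposure from a study in locally advanced or metastatic disease, whereas this trial plans about one year of adjuvant treatment. It also pools onset times across regimens, with no stated time origin. This stands, so 0.3 is the better guide for completers.

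A reader might also infer that counting ICE rather than CVA drops strokes the protocol intended to count. The documents do not support that. The search list is not shown. Protocol Appendix 6, which 8.10 cites, is largely ischemic in content, and Appendix 6 and Section 5.12.1 handle suspected TIA together with CVA. An ischemic list could drop hemorrhagic events, add TIA, or differ little, so neither the sign nor the size of that effect can be determined.

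**Conclusion.** The window mismatch is real and minor. SAP 7.4 summarises the protocol's only AESI to 30 days after last dose while the same SAP defines a 100-day period, uses it in the two preceding sections, and gives no reason for the difference. The by-arm count is lower than or equal to the extended-period count.

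Any shortfall is probably small: about 0.3 Arm A events for on-schedule completers and perhaps about 1 if treatment stopped early. These figures rest on the enrolment, rate and onset assumptions above. They would be lower if new anticancer therapy began early, because that closes both windows, and lower if risk falls once dosing stops.

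A reader might infer that the plan undercounts strokes or favours the combination arm. The documents do not show this. They report no CVA on days 31 to 100 after last dose, the same window applies in both arms, the effect on the difference between arms is not established, and no comparison between arms is planned.

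**What to change.** In SAP 7.4, add the by-arm AESI summary over the extended (100-day) treatment-emergent period already defined in 6.6, and keep the 30-day table as supportive. Have the search list cover all CVA events under protocol 8.10, with any non-ischemic or unspecified events on a separate line, so that the reader can see whether ICE and CVA differ in practice.

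The cost is one more table from data the protocol already collects. The drawback is that later events are harder to attribute to study drug, which is a reason to show both windows side by side.

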Overall, 1.9% (26 of 1345) of patients exposed to bempegaldesleukin reported CVA events. Of the 26 patients, 13 patients experienced Grade 3 or 4 events and 4 patients had a fatal outcome. The mean time to first CVA event was 218.7 days (range 4 to 727 days; median 158 days). Twenty of the 26 patients with CVA events received a doublet combination with a checkpoint inhibitor, which included 1.7% (19 of 1116) of patients who received nivolumab, 1.3% (1 of 76) who received pembrolizumab, and 0% (0 of 23) who received atezolizumab.

Based on these events, CVA was escalated to an adverse event of special interest (AESI) and mitigations were put in place to reduce the risk of CVA. These mitigations include implementation of a CVA adverse event management algorithm ([Appendix 6](#)) and updates to the exclusion criteria, renal function and hydration assessment, hydration guidelines, concomitant and prohibited medications, dose modification guidelines, and discontinuation criteria. Additional information on the clinical safety and risk of CVA is found in the bempegaldesleukin Investigator's Brochure.

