## 5.0 OVERALL STUDY DESIGN AND PLAN

### 5.1 Study Design

This is a multicenter, randomized, open-label, Phase 3 study that will evaluate the efficacy and safety of bempedaldesleukin(NKTR-214) plus Nivolumab compared with Nivolumab after complete resection of melanoma in patients at high risk for recurrence.

Approximately 950 patients with completely resected Stage IIIA (LN metastasis > 1 mm), IIIB/C/D, or IV ([AJCC 8th edition](#)) NED cutaneous melanoma will be randomized in a 1:1 ratio to the two treatment arms below:

- Arm A: bempedaldesleukin(NKTR-214) plus Nivolumab IV infusion q3w
- Arm B: Nivolumab IV infusion q4w

Randomization will be stratified by:

- PD-L1 status by Dako PD-L1 PharmDx 28-8 assay:  $\geq 1\%$  vs  $< 1\%$  vs indeterminate/not evaluable

[figure not shown]
Note: PD-L1 indeterminate/not evaluable will be capped at a maximum of 25% of the total

- Stage: IIIA (LN metastases > 1 mm)/IIIB vs IIIC vs IIID/IV

[Figure 1](#) displays the study schematic.

On April 14 2022, Nektar Therapeutics and Bristol-Myers Squibb jointly decided to end the global clinical development program for bempedaldesleukin in combination with Nivolumab. This study has been terminated from this decision. As of the date of announcement, approximately 774 patients were enrolled and the data for those patients will be limited due to early termination, thus not all analyses described in the protocol will be performed. The details for the planned analyses for this final CSR are included in [Section 6](#) and [Section 7](#).

Figure 1: Study Schematic

IV (when referring to treatment dose) = intravenous; LN = lymph node; NKTR-214 = bempagaldesleukin; PD-L1 = programmed cell death ligand 1; q3w = every 3 weeks; q4w = every 4 weeks; q6m = every 6 months; q12w = every 12 weeks.

- Patients will undergo Safety Follow-up Visits for 100 ( $\pm 7$ ) days after the last dose of study treatment and imaging assessments for up to 5 years from randomization.
- See Section 5.3 for other protocol-defined reasons for treatment discontinuation.
- Safety Follow-up 1: 30 ( $\pm 7$ ) days after the last dose of all study treatment(s).
- Safety Follow-up 2: 100 ( $\pm 7$ ) days after the last dose of all study treatment(s).
- Survival Follow-up: q12w ( $\pm 14$  days) following the Safety Follow-up Visit 2 (or 100 [ $\pm 7$ ] days after last dose of study treatment).

\* Nivolumab 4.5 mg/kg IV q3w for patients  $< 40$  kg.

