## 6.0 STATISTICAL CONSIDERATIONS

### 6.1 General Considerations

Summary statistics for continuous variables will include the mean, standard deviation, median, minimum, and maximum. The mean and median will be presented to one decimal place beyond which the data were captured. The standard deviation will be presented to two decimal places beyond which the data were captured. The minimum and maximum will be presented to the precision with which the data were captured.

Categorical variables will be presented as frequency counts and percentages. A row or column denoted 'Missing' will be included in count tabulations where necessary to account for dropouts and missing values. Percentages will be rounded to 1 decimal place and the percent will be suppressed when the count is zero. The denominator will be the number of patients in the population of interest unless otherwise noted.

Data listings will be created to support each table and to present all data. Data listings will be presented by treatment group and patient number.

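### SAP 7.4 reports ischemic cerebrovascular events as a crude percentage unlinked to time at risk; after early termination this is expected to understate the risk of the planned one-year course

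*SAP*

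**What the plan says.** SAP 7.4 names ICE as the bempegaldesleukin event of special interest. It sets the scope as "All analyses will be conducted in the Safety population by treatment arm using the treatment-emergent period" and plans two outputs:

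- a table: "Overall summary of ICE by worst CTC grade (any grade, grade 3-4, grade 5) presented by PT";
- a listing: "A by-patient listing of ICE will be provided".

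SAP 6.1 presents categorical data as counts and percentages and adds: "The denominator will be the number of patients in the population of interest unless otherwise noted". For patients off treatment, SAP 6.6 closes the treatment-emergent window at "30 days after the date of the last dose of any study treatment", or the day before new anticancer therapy if that is earlier.

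Exposure is summarised separately. SAP 6.10.2 covers duration, cycles and dose intensity, and SAP 6.7.1 adds a Kaplan-Meier curve of treatment duration that censors patients still on drug. Neither is linked to the ICE table. SAP section 7 contains no person-time rate, cumulative incidence or time-to-onset summary for any adverse event, and no confidence interval for ICE.

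The SAP was written after termination. Section 5.1 records that "approximately 774 patients were enrolled and the data for those patients will be limited due to early termination".

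**The concern.** A patient whose dosing was cut off after three weeks and one who completed a year carry equal weight in the denominator. When truncation is administrative and staggered, as it is when a programme closes during accrual, the share of patients with an event depends on how long they happened to be observed as well as on the drug.

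The SAP deals with the same truncation elsewhere. It plans Kaplan-Meier summaries with 6- and 12-month rates for OS, DMFS and PFS2 and for RFS by investigator (SAP 6.11.2.1 to 6.11.2.3 and 6.11.2.6), in the same Safety population. The main drug-specific harm gets no such estimate.

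This event was escalated to special-interest status. Protocol 2.1.3.2.5.2 reports 4 fatal outcomes among 26 patients with an event. Comparative analyses are cancelled and the DMC is dissolved, so the per-arm descriptive figures are what readers of the report will have. A bare low percentage without an interval is easily taken as the risk of the regimen as designed.

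**Working it through.** **Inputs from the documents.** 50 patients per month after a 7-month ramp-up, with 950 patients at 22.5 months (Protocol 9.2). About 774 enrolled at termination (SAP 5.1). At most 17 three-week cycles in Arm A or 13 four-week cycles in Arm B, so the last scheduled dose is 16 × 21 = 12 × 28 = 336 days after the first, day 337 in both arms. The ICE window adds 30 days, to day 367.

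**Assumptions not in the documents.** Actual accrual follows the plan with a linear ramp; dosing ends on the announcement date; the first dose is at randomization; 774 / 2 = 387 patients per arm, all treated; the hazard has one of two shapes.

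**Step 1: reproduce the planned accrual.** 0.5 × 50 × 7 + 50 × 15.5 = 175 + 775 = 950 at 22.5 months, as stated.

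**Step 2: time since entry at the cut** (30.4375 days per month).

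- Patient 774 enters at 7 + (774 − 175)/50 = 18.98 months.
- The median patient (387th) enters at 7 + (387 − 175)/50 = 11.24 months, so the median follow-up is 7.74 months, or 236 days.
- Day 337 is 11.07 months. Those who entered before month 7.91 have reached it: 175 + 50 × 0.91 ≈ 220 of 774, or 28%. The other 72% (about 554) are spread evenly over 0 to 337 days.

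**Step 3: expected crude percentage relative to full-course risk.** Ratio = mean of F(min(time since entry, 337) + 30) / F(367), where F is the cumulative risk up to a constant factor.

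- Constant hazard, F(t) proportional to t: mean time = (554 × 168.5 + 220 × 337)/774 + 30 ≈ 246 days; 246/367 = 0.67.
- Front-loaded, F(t) = 1 − 2^(−t/158): F(367) = 0.800. The mean F is 0.542 for the truncated group and 0.800 for the rest, giving (554 × 0.542 + 220 × 0.800)/774 ≈ 0.615; 0.615/0.800 = 0.77.
- Letting patients also stop treatment at the planned nivolumab RFS rates (90% at 3 months, 70.5% at 12 months) gives 0.69 and 0.79.

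The range under planned accrual is therefore 0.67 to 0.79. Uniform accrual over 12 to 24 months, with the same hazard and stopping options, gives 0.58 to 0.86.

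**Step 4: bias against sampling error.** No document gives a one-year risk. Suppose, only to set a scale, that it were 1.9%.

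- Expected full-course cases in Arm A: 387 × 0.019 = 7.4.
- Expected under truncation: 7.4 × 0.67 = 4.9 to 7.4 × 0.79 = 5.8.
- Crude percentage: 1.9 × 0.67 = 1.3% to 1.9 × 0.79 = 1.5%, a shortfall of 0.4 to 0.6 percentage points.
- Exact 95% CI for 5/387 = 1.3%: 0.4% to 3.0%.

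The interval is several times wider than the shortfall.

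**The case against.** The strongest reply is that the planned percentage is not wrong: it correctly states what happened during the exposure received, and the SAP never calls it a one-year risk. Patients who had finished or stopped before termination are unaffected. With a handful of cases, the listing and exposure summaries let a reader see each event and how long each arm was treated. All of this stands. What remains is that nothing planned turns these outputs into an estimate that allows for unequal observation, and no interval shows how little the count can say.

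Four stronger readings are tempting, and the documents do not support them.

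- *The result must fall below the programme's 1.9%.* That figure (26/1345 = 1.93%) is itself a crude percentage. At the same cutoff, PIVOT-02 supplied 557 of the 1345 patients (41%), with a median exposure of 106 days (Protocol 2.1.3.2.2). The pool also mixes combinations, includes this study and counts CVA events, whereas SAP 7.4 counts ischemic events from its own search list. Truncation need not put this trial below it.
- *CVA is shown to be a late harm.* The protocol states: "The mean time to first CVA event was 218.7 days (range 4 to 727 days; median 158 days". These are times among cases only, from a pool with varying follow-up and no stated time origin. A constant hazard over 367 days would put the median case near day 184, so 158 is not late, and it cannot fix the shortfall here.
- *The reported figure will be too low.* That holds only in expectation, and only if the figure is read as full-course risk. At ratios of 0.65 to 0.85, the chance of still seeing 8 or more cases in 387, if the full-course risk were 1.93%, is about 12% to 30%.
- *The arms are distorted against each other.* Both were cut at one calendar date, and the comparison is cancelled.

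**Conclusion.** The point holds as a limited one. The only aggregate ICE summary ignores time at risk, and this SAP was written knowing that exposure had been truncated. Read as risk over the planned course, the percentage is expected to be low: about 21% to 33% below under planned accrual, and about 14% to 42% below across the accrual patterns tried. Every scenario points the same way. The size is illustrative, because actual accrual, dosing stop dates, the arm split and the hazard shape are not given. Chance variation in 5 to 6 expected cases exceeds the bias, which argues for showing an interval rather than for leaving the figure bare.

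This is an inexpensive improvement to a descriptive safety report. It does not invalidate the planned table.

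**What to change.** In SAP 7.4, keep the crude table and the listing, and add by arm:

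1. Cumulative incidence of first ICE from first dose at 6 and 12 months with 95% CI, censoring at the end of each patient's adverse-event window or at data cutoff, with death as a competing event. Show numbers at risk: under planned accrual only about 28% would have reached day 337, so the 12-month estimate rests on few patients.
2. As a supplement, first-event incidence per 100 patient-years with 95% CI, noting that it assumes a constant hazard. If the hazard is front-loaded, it overstates the full-course rate: 0.77/0.67 ≈ 1.15 under the exponential shape above.
3. A sentence saying that the crude percentage describes events during the exposure received and is not an estimate of one-year risk.

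State which window the new table uses. ICE follows the 30-day window, while for the checkpoint-inhibitor events SAP 7.3 says "The following analyses will be conducted using the extended treatment-emergent period", which runs to 100 days.

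The cost is SAP wording and one table built from event-onset and dosing dates already collected. The downside is wide intervals. No dose or clinical rule changes.
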